8.2.2 Anticipated Procedure-related Adverse Events

	Document Type: Global Clinical	Page No: 13 of 59
	Title: Clinical Investigation Plan Study ID: UCC-23AC023	Version No: 1.0

Template GFM-10095B

Potential Risk of Clinical Significance	Summary of Data/Rational for Risk	Mitigation Strategy

 Potential discomfort due to full bladder. 	
 Participants will be asked to drink fluids in between voids to ensure a full second void. 	
 Participants who meet the eligibility criteria and follow study instructions should not have a bladder that is uncomfortably full.

 Potential biohazard exposure after use 	
 Device is intended to capture urine, may lead to transmission of bloodborne pathogens. 	
 Participants will be provided gowns and offered gloves during study participation

8.2.3 Additional Risks Associated with Study Participation

No additional risks associated with participation in this study have been identified.

8.3 Risk / Benefit Analysis

Taking into consideration the measures to minimize risk to subjects in this study, the potential risks identified in association with PureWick™ Male External Catheter and PureWick™ Flex Female External Catheter are justified by the anticipated benefits that may be afforded to subjects with requiring a non-invasive urine output management solution.

9.0 SUBJECTS

Adolescent male and female healthy participants will be recruited by the clinical site, TKL Research Inc. Participants will be recruited from the site's existing pool of volunteers in a database owned by the study site and with advertisements. It is anticipated to have 20 enrolled male and 20 enrolled female healthy volunteers aged 12-21 years old, with a target of 50% between 12-17 and 50% between 18-21. At least one male participant and one female participant must be the minimum age of 12, and at least one male participant and one female participant must be the maximum age of 21 to ensure representativeness across the target age range.

9.1 Inclusion Criteria

In order to be eligible to participate in this study, an individual must meet all of the following criteria:

1. Healthy Adolescent Male or Female aged 12 through 21 years old
2. Able to independently and voluntarily void urine
3. Ability to speak and understand English
4. Willing to comply with all study procedures in the protocol
5. Provision of signed and dated informed consent form.

9.2 Exclusion Criteria

Subjects are excluded from the study if any of the following criteria apply:

 BD	Document Type: Global Clinical	Page No: 14 of 59
	Title: Clinical Investigation Plan Study ID: UCC-23AC023	Version No: 1.0

Template GFM-10095B

1. Has urinary retention
2. Incontinent to feces
3. Has any irritation, wound, open lesion at the device application site
4. For females: currently menstruating without use of an internal device, e.g. tampon or menstrual cup, during the execution of the study
5. For females: currently pregnant at time of consenting (self-reported)
6. Currently enrolled in or has previously been enrolled in or has completed nursing or other clinical training and courses
7. Has ever been employed as a home health aide or homecare provider
8. Any other condition that, in the opinion of the investigator, would preclude them from participating in the study.

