4.2 Rationale

The purpose of this study is to understand if external catheters are an effective alternative in the adolescent population in both male and female adolescents in the setting where the external catheter is placed by a healthcare professional as well as in the outpatient or home setting where the external catheter is self-placed or placed by guardian/parent, and to provide data to support potential labeling for an expanded population use. Specifically, the study will collect data about how the external catheters perform in terms of capture rate when participants are voiding after self-placement of the device, if the adolescent participant can use the device independently or with the help of a guardian/parent and collect any adverse events that are reported.

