7.0 DESIGN OF THE STUDY

7.1 Overall Design

This prospective, uncontrolled, open-label, single-center, healthy volunteer study will assess the performance of the PureWick™ System in adolescents following a void with HCP placement of the device and a void with participant (or guardian/parent) placement of the device. Male participants will evaluate the PureWick™ Male External Catheter and female participants will evaluate the PureWick™ Flex Female External Catheter.

The expected participation time is approximately 2-3 hours, divided across two voids. Prior to the first void, each participant will be consented and trained on device instructions for use.

For each device evaluation, participants will have the device placed by a healthcare professional (HCP) for one void and will self-place the device for the other void. The participant may have a guardian or parent place the device only if the participant is unable or unwilling to self-place the device. With the device in place, participants will urinate two separate times during the study to evaluate the performance of the device in the adolescent population. After each void, the device will be removed by the HCP or self-removed (a guardian or parent may remove the device if the participant is unable or unwilling to remove the device). Finally, the participants will be asked to complete brief questionnaires to assess perceived wetness, IFU comprehension, comfort and ease of use. HCPs will also be asked to complete questions about ease of use for the voids in which they placed and removed the device.

Approximately 40 healthy participants (20 male and 20 female) will be enrolled into the study. The study will be conducted at one clinical site.

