1.7	
The HCP will perform a skin integrity check and note any existing signs or symptoms of irritation in the perineal area. If the participant's skin is compromised, the HCP will consult the site staff before proceeding with placement of study device and/or withdraw the participant.
 
HCP will confirm if no signs or symptoms of irritation in the perineal area was noted.

Steps	Activity 2 (Placement of device)
2.1	The participant will be given either the PureWick™ Male External Catheter (male participants only) or PureWick™ Flex Female External Catheter (female participants only).
2.2	For female participants only: The participant (or guardian/parent) or HCP will curve the PW Flex to fit the participant's anatomy per the IFU.
2.3	
The PW MEC or PW Flex will be connected to the canister via collector tubing per the IFU. Tubing connection to be done by the participant (or guardian/parent) for the self-placed void and by the HCP for the HCP-placed void. The HCP will confirm and record if the tubing connection was made correctly for the self-placed void. If the connection was not done correctly, the HCP will capture the reason:
 
 1. The participant did not understand how to make the connection 2. The participant connected the device to the wrong tubing port 3. The participant was not physically able to make the connection with sufficient force 4. Other, specify 
The HCP will adjust tubing connection prior to void if it was not done correctly.

2.4	Based off the randomization of placement sequence, the participant will self-place (or guardian/parent) the device or the HCP will place the device.
2.5	
If device was self-placed (or guardian/parent), the HCP will confirm the placement of the PureWick™ Male External Catheter (male participants only) or PureWick™ Flex Female External Catheter (female participants only). If the device is not placed correctly, the HCP will ask the participant to reposition/adjust the device. The HCP will record if any adjustments were made.
 
Even when placed correctly, participants may adjust the device as needed for comfort. The HCP will record if any adjustments were made.

Steps	Activity 3 (Void #1)
3.1	The HCP will confirm that the absorbent bed pad is appropriately positioned under the participant.
3.2	The participant will be asked to void in the supine position. The participant will be instructed not to strain or attempt to regulate their urine flow.

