11.4 Final Analysis

11.4.1 Primary Endpoint(s)

Capture Rate

Capture rate is defined as:

$$\frac{\text{weight of captured urine} \times 100\%}{\text{weight of captured urine} + \text{weight of urine leak}}$$

Voids with a total volume (captured urine + urine leak) of 10 mL is considered evaluable for this endpoint. Summary statistics such as mean, standard deviation, median, and range will be used for the analysis of capture rate. Separate summary may be provided by gender and by placement (HCP or self).

Perception of Wetness

Response to the questionnaire will be summarized as categorical variable and as continuous variable. Summary statistics such as frequency count, mean, standard deviation, median, and range will be provided. Separate summary may be provided by gender and by placement (HCP or self).

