2.2 Efficacy Data Summary of Figures and Tables

2.2.1 Treatment summary

Note that some questions on treatment CRF are device specific or placement specific:

Self-placed void only:

- Did the guardian/parent help the participant place the device?
- Was the device correctly connected to canister via collector tubing?
- Did HCP feel the catheter was correctly placed?
- Was catheter repositioned by participant after placement?

PureWick Flex Female only:

- Did the catheter move or become dislodged?

For percentages, the total number of non- missing data counts will be used as the denominator.

	Title: UCC-23AC023 Statistical Analysis Plan Table shells	Page No.
	10 of 33	
	Study Title: UCC-23AC023 PureWick Adolescent Study	Version No:
	CIP/CPSP Version: 1.0	1.0

Template GFM-10082B

Table 5 Treatment Summary by Void
ITT

	Void 1 (N = xx)	Void 2 (N = xx)
Device Placed by		
Self Placed	n/N(%)	n/N(%)
HCP	n/N(%)	n/N(%)
Did Subject Participate in Device Placement/Void Attempt		
Yes	n/N(%)	n/N(%)
No	n/N(%)	n/N(%)
Any Signs of Injury or Irritation in The Perineal Region Prior to Device Placement		
Yes	n/N(%)	n/N(%)
No	n/N(%)	n/N(%)
Was Device Placed		
Yes	n/N(%)	n/N(%)
No	n/N(%)	n/N(%)
Device		
PureWick Flex Female	n/N(%)	n/N(%)
PureWick Male	n/N(%)	n/N(%)
Did the Guardian/Parent Help the Participant Place the Device		
Yes	n/N(%)	n/N(%)
No	n/N(%)	n/N(%)
Was the Device Correctly Connected to Canister via Collector Tubing		
Yes	n/N(%)	n/N(%)
No	n/N(%)	n/N(%)
Did HCP feel the catheter was correctly placed		
Yes	n/N(%)	n/N(%)
No	n/N(%)	n/N(%)

	Title: UCC-23AC023 Statistical Analysis Plan Table shells	Page No.
	11 of 33	
	Study Title: UCC-23AC023 PureWick Adolescent Study	Version No:
	CIP/CPSP Version: 1.0	1.0

Template GFM-10082B

Was Catheter Repositioned by Participant After Placement		
Yes	n/N(%)	n/N(%)
No	n/N(%)	n/N(%)
Did the Participant Have a Void		
Yes	n/N(%)	n/N(%)
No	n/N(%)	n/N(%)
Did the catheter move or become dislodged		
Yes	n/N(%)	n/N(%)
No	n/N(%)	n/N(%)
Was There Any Leakage Observed by HCP After the Void		
Yes	n/N(%)	n/N(%)
No	n/N(%)	n/N(%)
Are There Any Signs of Injury or Irritation in the Perineal Region or Adverse Reactions After Device Removal		
Yes	n/N(%)	n/N(%)
No	n/N(%)	n/N(%)
Pad Starting Weight (g)		
N	XXX	XXX
Mean (SD)	xx.x (xx.x)	xx.x (xx.x)
Median	xx.x	xx.x
Min – Max	XXX-XXX	XXX-XXX
Pad Final Weight (g)		
N	XXX	XXX
Mean (SD)	xx.x (xx.x)	xx.x (xx.x)
Median	xx.x	xx.x
Min – Max	XXX-XXX	XXX-XXX
Canister Starting Weight (g)		
N	XXX	XXX

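### The exclusions for clinical training and home-care work do not reach the guardian or parent who may place the device, and that person's background is not recorded

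*Protocol*

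**What the plan says.** The eligibility list in Protocol 9.2 opens with "Subjects are excluded from the study if any of the following criteria apply". Criterion 6 reads "Currently enrolled in or has previously been enrolled in or has completed nursing or other clinical training and courses" and criterion 7 reads "Has ever been employed as a home health aide or homecare provider". The synopsis repeats both. Neither mentions a guardian or parent.

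Protocol 7.1 provides a fallback: "The participant may have a guardian or parent place the device only if the participant is unable or unwilling to self-place the device". Section 7.1 gives the same fallback for removal, and step 2.3 of section 10.4 lets the guardian make the tubing connection. Step 2.4 treats the guardian's placement as part of the self-placement condition: "the participant will self-place (or guardian/parent) the device or the HCP will place the device".

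Protocol 4.2 says what the non-HCP void stands for: use "in the outpatient or home setting where the external catheter is self-placed or placed by guardian/parent". The analysis has two placement categories only. Protocol 11.4.1 says "Separate summary may be provided by gender and by placement (HCP or self", and SAP Tables 6, 9a, 9b and 11 have HCP and self-placed columns.

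The SAP (2.2.1) lists one relevant CRF item for self-placed voids, "Did the guardian/parent help the participant place the device". It appears in Tables 5 to 7 and in Listing 8. Neither document provides for recording the guardian's training or employment.

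**The concern.** The documents give no reason for criteria 6 and 7. Neither describes a safety risk to the wearer. The natural reading, given section 4.2, is that they keep the non-HCP void representative of someone without clinical training. On that reading the criteria should follow the hands that do the work. Instead they screen the adolescent, who at 12 to 17 (the target for half the sample) is unlikely to have such training, and pass over the adult who may place the device and has had years to acquire it.

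A parent who is a nurse or home health aide could therefore connect, place and remove the device, and the result would enter the self-placed columns unmarked. What is at stake is how far those columns, with 20 voids per device, can be read as evidence of lay use in support of the expanded labeling.

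**Working it through.** The plan states no figure on this point, so there is none to reproduce. The check has two parts.

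**1. The text, set side by side**

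| Question | Participant | Guardian or parent |
|---|---|---|
| Screened for training or home-care work? | Yes (9.2, items 6 and 7) | No |
| May connect, place, remove? | Yes (10.4, steps 2.3, 2.4, 4.1) | Yes (7.1; same steps) |
| Void reported as | Self-placed | Self-placed |
| Involvement recorded? | By default | Yes/No for help with placement (SAP 2.2.1, Listing 8) |
| Background recorded? | Through eligibility | No |

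The outcomes are not equally exposed:

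- *Capture rate and wetness* are measured after the HCP has checked the self-placed void. Under step 2.3 the HCP corrects a wrong tubing connection, and under step 2.5 asks for repositioning if placement is wrong.
- *Connection correct* and *placement correct* (Table 6, self-placed column only) describe the placer's own performance. Step 2.3 has the connection recorded and then adjusted. For placement, the order of step 2.5 implies the same, though the time of recording is not stated.
- *Ease-of-use ratings* (Table 12) are given by the participant after the self-placement void and may describe a guardian's work.

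**2. Size, on assumed values**

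From the documents: 20 participants per sex, one self-placed void each, so n = 20 per device and 40 overall. One void is 1/20 = 5.0% of a device's self-placed voids and 1/40 = 2.5% of all of them.

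Not in the documents, so assumed: g, the guardian-placed voids per device (2 to 5); p, the share of guardians who are clinically trained (5% to 15%); d, the capture-rate advantage of a trained placer (5 to 20 points).

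*Chance of at least one such void* = 1 − (1 − p)^g:

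| | p = 5% | p = 10% | p = 15% |
|---|---|---|---|
| g = 2 | 9.8% | 19.0% | 27.8% |
| g = 5 | 22.6% | 41.0% | 55.6% |

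Over both devices (2g voids) the range is 1 − 0.95^4 = 18.5% to 1 − 0.85^10 = 80.3%. These are chances that such a void occurs, not sizes of bias.

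*Shift in a device's self-placed mean capture rate* = (k/20) × d for k such voids:

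| k | d = 5 | d = 10 | d = 20 |
|---|---|---|---|
| 1 | 0.25 | 0.5 | 1.0 |
| 2 | 0.5 | 1.0 | 2.0 |
| 5 | 1.25 | 2.5 | 5.0 |

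The row k = 5 needs every guardian at the top of the assumed range to be trained, so it is an extreme.

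*Less protected items.* One void that changes from incorrect to correct moves the Table 6 proportion by 1/40 = 2.5 percentage points, and the same item by device (Table 7) by 1/20 = 5 points. One ease-of-use rating that rises by one category moves a device mean by 1/20 = 0.05 on the 5-point scale.

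**The case against.** The case on the other side is substantial.

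- **The HCP check.** The participant is trained from the IFU and a video, and self-placed voids proceed after an HCP check and any correction. A skilled guardian has little left to add to either primary endpoint. This stands for capture rate and wetness, but not for what is recorded before correction or for the ease-of-use ratings.
- **Guardian placement is intended.** The primary objective includes it, and it is a fallback only. Some guardians in real home use will have such training. This stands: pooling guardian and self-placement is planned, and the point is only the unscreened and unrecorded background.
- **No conclusion is tested.** There is no performance goal (Protocol 6.2) and no hypothesis test (11.0), so no pre-specified decision would change. This stands and limits the weight of the point.

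A reader might also infer four stronger things that the documents do not support:

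- *That a trained guardian turns the self-placed void into a second HCP placement.* This ignores the HCP check, which already narrows the gap between placers.
- *That the data could never reveal the problem.* Listing 8 identifies guardian-helped voids and Listing 10 gives capture rate for the same subject and void, so results can be seen without them. What is lost is the split between trained and lay guardians. Such a summary also drops the participants who could not or would not self-place, and the CRF item asks only about placement, not connection or removal.
- *That the bias is known to favor the device.* That direction is plausible, but no data in the documents establish it.
- *That such voids should be deleted from Tables 9b and 11.* Those tables are ITT, defined in Protocol 11.2 as everyone with a device placed for at least one void. Participants are not replaced (9.5.1), and 20 per sex is a stated minimum (11.1).

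**Conclusion.** The gap is real and is present in the current text of both documents: criteria 6 and 7 do not cover the person who may connect, place and remove the device, and that person's background is recorded nowhere. That the criteria are there to protect lay representativeness is an inference, though a natural one.

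The likely effect on the primary endpoints is small: 0.25 to 1.0 point in a device's mean capture rate for one such void, if a trained placer gains 5 to 20 points. The frequency of guardian placement, the share of trained guardians and that gain are all assumptions. The connection and placement checks and the ease-of-use ratings are more exposed, at 2.5 to 5 percentage points per void for the two checks. The point concerns how the self-placed results can be interpreted. It does not show that the primary results would be wrong. It is worth settling before enrollment because the remedy is cheap and the study has a single visit, after which the background may be hard to recover.

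**What to change.** 1. **Protocol 9.2.** Add a sentence: a guardian or parent who meets criterion 6 or 7 should not act as placer where another guardian or self-placement is possible. Mirror it in the synopsis.
2. **Treatment CRF and Listing 8.** Record who placed the device (participant or guardian) and, for a guardian, whether criterion 6 or 7 applies.
3. **SAP.** Keep all voids in the ITT tables. Add a sensitivity summary of the self-placed columns of Tables 6, 9b and 11 without voids placed by a clinically trained guardian. If background is not collected, leave out all guardian-helped voids and state that this also removes lay guardians.

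The cost is a small addition to the CRF, one extra summary, and an occasional participant who needs a different guardian. Because the restriction applies only where an alternative exists, it need not cost a participant the self-placed void.

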9.3 Vulnerable Subjects

Human subject regulations consider pediatric subjects a vulnerable population. This study will require IRB review and approval prior to the start of the study. Prior to approval, the IRB must determine that no greater than minimal risk to children is presented in the study. Written informed consent using the IRB approved consent form will be obtained from all subjects or their parent/guardian prior to participating in the study. The IRB will determine if assent of the adolescent participants is required in addition to parent/guardian consent. No medical care will be provided to the study participants once the study has been completed.

9.4 Point of Enrollment

The point of enrollment is the time at which, following recruitment and before any clinical investigation-related procedures are undertaken, a subject signs and dates the informed consent form.

9.4.1 Point of Treatment

Once the participant meets all the eligibility criteria and signs the ICF, the participant is considered enrolled and study activities will begin as outlined in section 10.

9.4.2 Point of Randomization

Randomization assignment should occur only when all eligibility criteria are met and consent has been obtained. The point of randomization is after enrollment when the site assigns a subject to a device placement order per the Sponsor provided randomization list.

9.5 Screen Failures and Replacement of Subjects

Screen failures are defined as subjects who consent to participate in the clinical study but are not subsequently randomized into the study. Demographic information may be captured for screen failures. Screen failures will not be allowed to re-screen.

The Principal Investigator will maintain a screening log to record details of all subjects screened and to confirm eligibility or record reasons for screening failure, as applicable.

9.5.1 Replacement of Subjects

	Document Type: Global Clinical Title: Clinical Investigation Plan Study ID: UCC-23AC023	Page No: 15 of 59
		Version No: 1.0

Template GFM-10095B

Not Applicable – This study will not have replacement participants.

9.6 Study / Participation Duration

- 9.6.1 It is expected to take approximately 2-3 weeks to complete subject enrollment. The total duration of the study is expected to be 2-3 weeks (last subject, last visit).
- 9.6.2 The duration of study participation for an individual subject is expected to be approximately 2-3 hours (enrollment through last study assessment).

9.7 Subject Discontinuation / Withdrawal [and Discontinuation of Intervention]

9.7.1 Discontinuation / Withdrawal

- 9.7.1.1 A subject may withdraw from the study at any time at their own request or may be withdrawn at any time at the discretion of the Principal Investigator (PI) or sponsor for safety, behavioral, compliance, or administrative reasons. This is expected to be uncommon.
- 9.7.1.2 At the time of discontinuing from the study, no further assessments will be performed.
- 9.7.1.3 If the subject withdraws consent for disclosure of future information, the sponsor may retain and continue to use any data collected before such a withdrawal of consent.
- 9.7.1.4 If a subject withdraws from the study, they may request destruction of any samples taken and not tested, and the Principal Investigator must document this in the clinical site study records.
- 9.7.1.5 Once the study has ended, there will be no additional care for study participants.
- 9.7.1.6 There will be no additional procedures/parameters in the study.

